Data from the G142 study indicate that the G100 intratumoral dose of 20 μ g is relatively safe with only grade 1 or 2 related AEs reported and no DLTs and that this higher dose appears to induce greater numbers of infiltrating CD8 T cells into the tumor. Recent preclinical data indicate that G100 doses greater than 20 μ g can lead to improved survival of animals in tumor models, further supporting that additional dose exploration may be warranted. Therefore this arm will examine escalating doses of G100 plus rituximab in a single tumor site utilizing a 3+3 design in order to establish safety and examine clinical and biomarker responses. Once the highest safe dose/systemic exposure is determined, from the Dose Escalation portion of the study, all safety, efficacy and biomarker data will be reviewed by the Sponsor (in collaboration with the independent DMC) and either the highest dose determined to be safe or the most biologically active and safe dose (if different than the MTD) will be chosen for further investigation. A Patient Expansion group would then begin. Details of Dose Escalation and Patient Expansion are described below.

Part 5, Dose Escalation :

In the Dose Escalation portion, safety and efficacy of G100 injected into a single tumor lesion without radiation will be assessed using a 3+3 design where patients will be assigned to

sequential cohorts of escalating doses of intratumoral G100 in combination with standard dose induction therapy with rituximab. (Figure 8) Treatment will begin on Day 0 with rituximab 375mg/m² IV and continue weekly for a total of 4 doses. If there are no DLTs or significant safety events after the first dose of rituximab, G100 will be injected intratumorally beginning on Day 1, and then dosing will continue weekly for 3 additional doses (4 total) on a visit schedule that coincides with rituximab treatments as long as the tumor remains of sufficient size for injection. One lesion will be targeted to receive each dose of G100. If the lesion regresses, another lesion will be chosen for treatment. Imaging assisted injections are allowed but the feasibility and safety of these treatments must be discussed first and approved by the Medical Monitor. If the tumor lesion has not regressed completely after the first 4 doses of G100, dosing may continue for 2 additional weekly intratumoral doses (6 total). Following restaging, the patient may be eligible for a second course of G100.

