Four cohorts G100 plus rituximab are planned and will be enrolled sequentially:

- Cohort 1: G100 20 µg in single tumor lesion
- Cohort 2: G100 40 µg in a single tumor lesion
- Cohort 3: G100 60 µg in a single tumor lesion
- Cohort 4: G100 80 µg in a single tumor lesion

Initially, 3 patients will be scheduled to receive G100 at the first dose level. Dose escalation will be contingent upon acceptable safety data obtained during the first 28 days of observation following initiation of the regimen. A dose level cohort will be expanded from 3 to 6 if one of the first 3 patients experiences a dose-limiting toxicity (DLT). Further patient accrual into that dose level cohort (or higher) will be suspended as soon as ≥2 patients in that cohort experience DLT, or when otherwise deemed clinically appropriate by the investigator or Sponsor. After the 28-day DLT observation period for the final patient in a cohort is complete, if less than one third of the patients enrolled in that cohort developed a DLT, advancement to the next dose-level cohort can begin.

During Dose Escalation, patients will be considered evaluable for determination of safety and dose-level cohort advancement if they have received at least 3 complete G100 treatments and 3 doses of rituximab and have completed Day 28 safety monitoring OR have experienced DLT. Patients who experienced DLT during the safety period will not be replaced. All other patients who have not received at least 3 G100 treatments and 3 doses of rituximab and/or do not complete the Day 28 safety monitoring period for reasons other than treatment-related toxicity will be replaced. Based on ongoing evaluation of study data, the Sponsor may decide to complete fewer than the planned 4 dose cohorts and proceed directly to the Patient Expansion portion of the study.

Following completion of the dose escalation stage of the trial, the maximum tolerated dose (MTD) will be defined as the highest dose reached in which less than one third of the patients in

Immune Design

G100 (GLA-SE) and Pembrolizumab or Rituximab

Protocol IMDZ-G142; Version 04B, November 15, 2018

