6.2 Dose-Limiting Toxicities

DLTs will be used to establish safety parameters for stopping dose escalation and will follow a standard 3+3 study design. AE severity assessments will be performed using National Cancer Institute (NCI) Common Terminology Criteria for Adverse Events (CTCAE) v4.03 or newer. Unacceptable toxicity is defined when two or more subjects in a dose level cohort develop DLTs

considered at least possibly related to the study regimen. Further dosing at that level will be discontinued. Hospitalizations primarily intended to expedite diagnostic evaluations or for elective surgery will not be considered as SAEs for the purpose of ascertaining DLT. The occurrence of any of the following toxicities during the first 28 days will be considered a DLT, if assessed by the investigator to be possibly, probably, or definitely related to any component of study treatment (G100, pembrolizumab, or rituximab).

1. Grade 4 nonhematologic toxicity (not laboratory)
2. Grade 4 hematologic toxicity lasting \geq 7 days, except thrombocytopenia:
 - Grade 4 thrombocytopenia of any duration
 - Grade 3 thrombocytopenia associated with clinically significant bleeding
3. Any nonhematologic AE \geq Grade 3 in severity should be considered a DLT, with the following exceptions: Grade 3 fatigue lasting \leq 3 days; Grade 3 diarrhea, nausea, or vomiting without use of anti-emetics or anti-diarrheals per standard of care; Grade 3 rash without use of corticosteroids or anti-inflammatory agents per standard of care.
4. Any Grade 3 or Grade 4 nonhematologic laboratory value if:
 - Clinically significant medical intervention is required to treat the subject, or
 - The abnormality leads to hospitalization, or
 - The abnormality persists for >1 week.
 - The abnormality results in a Drug induced Liver Injury (DILI)
 - Exceptions: Clinically nonsignificant, treatable, or reversible laboratory abnormalities including liver function tests, uric acid, etc.
5. Febrile neutropenia Grade 3 or Grade 4:
 - Grade 3 is defined as ANC $<1000/\text{mm}^3$ with a single temperature of >38.3 degrees C (101 degrees F) or a sustained temperature of ≥38 degrees C (100.4 degrees F) for more than 1 hour
 - Grade 4 is defined as ANC $<1000/\text{mm}^3$ with a single temperature of >38.3 degrees C (101 degrees F) or a sustained temperature of ≥38 degrees C (100.4 degrees F) for more than 1 hour, with life-threatening consequences and urgent intervention indicated.

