6.4 Maximum Tolerated Dose/Maximum Safe Dose

The MTD will be defined as the highest G100 dose level studied in which less than one third of patients in a cohort experience DLT. If the MTD is declared at the final dose level, the highest dose will be considered the maximum safe dose examined in the study.

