8.1.8.4 Dose Modification, Warning and Precautions for Rituximab

Approved regulatory rituximab labeling and institutional guidelines for contraindications, warnings and precautions should be followed. Some of them are briefly summarized below.

Infusion Reaction

Rituxan can cause severe, including fatal, infusion reactions. Severe reactions typically occurred during the first infusion with time to onset of 30–120 minutes. Rituxan-induced infusion reactions and sequelae include urticaria, hypotension, angioedema, hypoxia, bronchospasm, pulmonary infiltrates, acute respiratory distress syndrome, myocardial infarction, ventricular fibrillation, cardiogenic shock, anaphylactoid events, or death.

Premedicate patients with an antihistamine and acetaminophen prior to dosing. Institute medical management (e.g., glucocorticoids, epinephrine, bronchodilators, or oxygen) for infusion reactions as needed. Depending on the severity of the infusion reaction and the required interventions, temporarily or permanently discontinue rituximab. Resume infusion at a minimum 50% reduction in rate after symptoms have resolved. Closely monitor the following patients: those with pre-existing cardiac or pulmonary conditions, those who experienced prior cardiopulmonary adverse reactions, and those with high numbers of circulating malignant cells ($\geq 25,000/\text{mm}^3$).

Tumor Lysis Syndrome

Acute renal failure, hyperkalemia, hypocalcemia, hyperuricemia, or hyperphosphatemia from tumor lysis, some fatal, can occur within 12–24 hours after the first infusion of rituximab in patients with NHL. A high number of circulating malignant cells ($\geq 25,000/\text{mm}^3$) or high tumor burden, confers a greater risk of TLS. Administer aggressive intravenous hydration and anti-hyperuricemic therapy in patients at high risk for TLS. Correct electrolyte abnormalities, monitor renal function and fluid balance, and administer supportive care, including dialysis as indicated.

Severe Mucocutaneous Reactions

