### **4.2 Safety Population**

The Safety Population includes all enrolled patients who received at least one injection of G100 after standard local radiation. Safety data analyses will be conducted on all patients in the Safety Population according to the treatment received.

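### In Part 5, a DLT after rituximab alone and before any G100 counts, read literally, toward stopping escalation and toward an MTD expressed as a G100 dose.

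*Protocol*

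**What the plan says.** Protocol 6.1 (Part 5, Dose Escalation) sets the order of treatment: "Treatment will begin on Day 0 with rituximab 375mg/m² IV and continue weekly for a total of 4 doses". G100 follows a day later, under a condition: "If there are no DLTs or significant safety events after the first dose of rituximab, G100 will be injected intratumorally beginning on Day 1". The text therefore foresees a DLT before any G100.

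The counting rules are these.

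- **Attribution (6.2).** A qualifying event in the first 28 days is a DLT if it is "possibly, probably, or definitely related to any component of study treatment (G100, pembrolizumab, or rituximab". Nonhematologic events of Grade 3 or higher qualify. The exceptions cover fatigue, diarrhea, nausea, vomiting and rash, not infusion reactions. Toxicity that ends treatment in Cycle 1 also qualifies.
- **Cohort (10.2).** Patients are assigned to a Part 5 cohort at enrollment.
- **Evaluability and replacement (6.1).** A DLT by itself makes a patient evaluable. "Patients who experienced DLT during the safety period will not be replaced".
- **Stopping (6.1, 6.3).** Two patients with a DLT suspend that level and those above it.
- **MTD (6.4).** "The MTD will be defined as the highest G100 dose level studied in which less than one third of patients in a cohort experience DLT".

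On rituximab itself, Protocol 8.1.8.4 warns: "Severe reactions typically occurred during the first infusion with time to onset of 30–120 minutes".

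For reporting, SAP 4.2 begins: "The Safety Population includes all enrolled patients who received at least one injection of G100". It adds that the injection follows standard local radiation. SAP 5.7 bases the safety evaluation, DLT tables included, on that population.

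**The concern.** Counting toxicity from either drug is normal for a combination once the combination has been given. The difficulty here is narrower. An event on Day 0, before the first injection, has the same probability whether the patient is in the 20 or the 80 µg cohort. It carries no information about the G100 dose, yet it enters a quantity defined as a G100 dose level.

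Three things follow.

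- The G100 MTD can be set too low. The expansion dose must be one judged safe, so it can be too low as well.
- The optional split-lesion cohort (6.1, Part 5 Patient Expansion; also 4.7) asks whether DLTs attributed to injecting a single lesion can be avoided by dividing the dose. It could open on DLTs that involved no injection.
- A patient who counted in the 3+3 can be missing from the SAP's DLT summary. The SAP lists tables of events related to G100 and to pembrolizumab but none for rituximab, so these events could not be separated by cause.

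**Working it through.** **The plan's own figure.** Protocol 6.1 gives 12-24 patients for Part 5 escalation: 4 cohorts × 3 = 12 and 4 × 6 = 24. This reproduces. The one-third threshold also fits the two-DLT rule: 1/6 is below one third and 2/6 is not.

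**The rules applied to one patient.** A patient assigned to the 60 µg cohort has a Grade 3 infusion reaction on Day 0. It is related to a component, falls within 28 days and is not an excepted event, so it is a DLT. The patient is evaluable, is not replaced, and counts among those enrolled in the cohort. A second such patient suspends 60 µg and above. The MTD is then at most 40 µg, although neither patient had received G100 when the DLT occurred. No section exempts a DLT that precedes the first G100 dose.

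**Size.** The documents give no rate for such events, so let r be the assumed chance per patient, with G100 causing no DLT. Each cohort is taken as a plain 3+3, without the optional three extra patients at 80 µg, and patients as independent.

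- P(cohort passes) = (1−r)³ + 3r(1−r)² × (1−r)³
- P(at least one of four cohorts stops) = 1 − P(passes)⁴
- P(expansion from 3 to 6) = 3r(1−r)²

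At r = 0.05, P(passes) = 0.8574 + 0.1354 × 0.8574 = 0.9734. A cohort stops with probability 0.0266, and 1 − 0.9734⁴ = 0.102.

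| r (assumed) | One cohort stops | At least one of four stops | A cohort expands to 6 |
|---|---|---|---|
| 2% | 0.5% | 1.8% | 5.8% |
| 5% | 2.7% | 10.2% | 13.5% |
| 10% | 9.4% | 32.6% | 24.3% |

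If G100 also has its own DLT rate q, independent of r, the combined rate is 1 − (1−q)(1−r). With q = 5% and r = 10% it is 1 − 0.95 × 0.90 = 14.5%, and at least one of four cohorts stops in about 54% of trials. With q = 5% and no pre-G100 events the figure is 10.2%.

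**Reporting, side by side.** Protocol 14.3.1 includes anyone given an injection of study drug or a study-related procedure. SAP 4.2 requires a G100 injection, and so does Protocol 4.7 in describing the safety data set, so the protocol is not at one with itself. SAP 4.2 also requires prior radiation, which Parts 4 and 5 omit. Read literally, that would exclude every Part 5 patient.

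**The case against.** Attribution to any component looks deliberate. Section 6.2 names all three drugs, Part 5 studies a combination, and the observation period runs from the start of the regimen. The error is toward caution, in a part described as exploratory. All of this stands, and it lowers the severity. It does not explain why an event before any G100 should define a G100 dose.

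The rates are assumptions, and the plan takes precautions. Exclusion 13 bars Part 5 patients with a history of significant reaction to anti-CD20 antibodies, and 8.1.8.3 requires premedication and a stepped first infusion. This argues for the lower end of the range; the documents offer no support for 10%.

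Three stronger inferences are tempting and should be resisted.

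- *A reader might infer that such a patient never receives G100.* Section 6.1 sets a condition for starting on Day 1. Section 6.5 allows case-by-case consideration of further G100 injections after a DLT, though it is unclear whether a first injection is meant. The DLT counts either way.
- *A reader might infer that the DMC cannot intervene.* Section 6.3 provides for DMC review and lets the Sponsor stop or continue where the DMC and investigator disagree on relationship to study agent or on clinical relevance. Section 4.7 gives the DMC a voice in determining DLTs and allows modifications after review. These are plausible routes, but none removes the event from the count in 6.4.
- *A reader might infer that the event is lost from the report.* SAP 5.1 lists the collected data, and SAP 5.7.2 puts all adverse events in listings. The gap is in the summary tables.

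**Conclusion.** The point holds as a conflict between how DLTs are counted and what the G100 MTD is said to mean. Taken together, the rules count a rituximab-only DLT that precedes any G100, and nothing exempts it. It should be fixed, but it is not critical: the bias is cautious, the part is exploratory, and DMC and Sponsor review would see the events.

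The size cannot be established from the documents. The 1.8% to 32.6% range rests on assumed rates of 2% to 10%, no DLTs from G100, independent patients and four plain 3+3 cohorts. It shows how sensitive the rule is and is not a forecast. A reader might infer that rituximab reactions are likely to decide the MTD; the documents do not support that.

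The reporting mismatch needs no assumed rate. As written, the SAP's DLT summary can omit a patient who counted in the escalation decision. SAP section 9 refers to termination of the study by the sponsor, which may limit the practical effect, but the inconsistency remains.

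**What to change.** **Protocol.** Reconcile 6.1 (Part 5 escalation and the split-lesion paragraph), 6.2, 6.3, 6.4 and the matching synopsis text, so that the count behind the G100 MTD agrees with its stated meaning as a G100 dose level. The text should say explicitly how a DLT before the first G100 dose is treated. The sponsor and DMC should decide how such events bear on suspension of dosing; no rule is proposed here. All such events should continue to be reported to the DMC.

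**SAP 4.2.** Align the Safety Population with Protocol 14.3.1, so that every Part 5 patient given rituximab or G100 is included, and remove the radiation condition where no radiation is given. Bring the safety data set wording in Protocol 4.7 and the synopsis into line.

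**SAP 5.7.2.** Show pre-G100 DLTs as a separate row and add tables of rituximab-related treatment-emergent events, so that the DLT summary matches the escalation decisions.

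**Cost.** A few sentences, one table row, one added set of tables and possibly an occasional replacement patient.

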6.2 Dose-Limiting Toxicities

DLTs will be used to establish safety parameters for stopping dose escalation and will follow a standard 3+3 study design. AE severity assessments will be performed using National Cancer Institute (NCI) Common Terminology Criteria for Adverse Events (CTCAE) v4.03 or newer. Unacceptable toxicity is defined when two or more subjects in a dose level cohort develop DLTs

considered at least possibly related to the study regimen. Further dosing at that level will be discontinued. Hospitalizations primarily intended to expedite diagnostic evaluations or for elective surgery will not be considered as SAEs for the purpose of ascertaining DLT. The occurrence of any of the following toxicities during the first 28 days will be considered a DLT, if assessed by the investigator to be possibly, probably, or definitely related to any component of study treatment (G100, pembrolizumab, or rituximab).

1. Grade 4 nonhematologic toxicity (not laboratory)
2. Grade 4 hematologic toxicity lasting \geq 7 days, except thrombocytopenia:
 - Grade 4 thrombocytopenia of any duration
 - Grade 3 thrombocytopenia associated with clinically significant bleeding
3. Any nonhematologic AE \geq Grade 3 in severity should be considered a DLT, with the following exceptions: Grade 3 fatigue lasting \leq 3 days; Grade 3 diarrhea, nausea, or vomiting without use of anti-emetics or anti-diarrheals per standard of care; Grade 3 rash without use of corticosteroids or anti-inflammatory agents per standard of care.
4. Any Grade 3 or Grade 4 nonhematologic laboratory value if:
 - Clinically significant medical intervention is required to treat the subject, or
 - The abnormality leads to hospitalization, or
 - The abnormality persists for >1 week.
 - The abnormality results in a Drug induced Liver Injury (DILI)
 - Exceptions: Clinically nonsignificant, treatable, or reversible laboratory abnormalities including liver function tests, uric acid, etc.
5. Febrile neutropenia Grade 3 or Grade 4:
 - Grade 3 is defined as ANC $<1000/\text{mm}^3$ with a single temperature of >38.3 degrees C (101 degrees F) or a sustained temperature of ≥38 degrees C (100.4 degrees F) for more than 1 hour
 - Grade 4 is defined as ANC $<1000/\text{mm}^3$ with a single temperature of >38.3 degrees C (101 degrees F) or a sustained temperature of ≥38 degrees C (100.4 degrees F) for more than 1 hour, with life-threatening consequences and urgent intervention indicated.
6. Prolonged delay (>2 weeks) in initiating Cycle 2 due to treatment-related toxicity.
7. Any treatment-related toxicity that causes the participant to discontinue treatment during Cycle 1.
8. Grade 5 toxicity.
9. Missing $>25\%$ of study drug doses as a result of treatment-related AE(s) during the first cycle.

6.3 Stopping Rules

During the initial 28-day treatment period, dosing will be suspended at any dose level (and higher) if DLTs are observed in 2 or more patients during Part 1 or during Dose Escalation of Part 4 or Part 5. During patient expansion of Parts 2, 3, 4 and 5, dosing will be suspended if DLTs considered at least possibly related to any study medication are observed during the first 28 days in one third or more patients within a group receiving the same treatment (assuming a minimum of 6 patients receiving the same dose and treatment regimen and would represent the initial denominator: In Parts 2 and 3, G100 alone; in Parts 2 and 4, G100/pembrolizumab, in Part 5, G100/rituximab)

All AEs and DLTs observed during dose escalation of any treatment arm and/or patient expansion meeting the criteria of a stopping rule will be reviewed by the DMC. If there is disagreement between the DMC and the investigator's assessment regarding the relationship of the event to study agent or to the clinical relevance (e.g., lab abnormality), the Sponsor in consultation with the DMC may determine to stop the treatment or continue. In the later case, the AE may become a medical event of interest and be tracked closely for additional events occurring in the future with intratumoral G100.

6.4 Maximum Tolerated Dose/Maximum Safe Dose

The MTD will be defined as the highest G100 dose level studied in which less than one third of patients in a cohort experience DLT. If the MTD is declared at the final dose level, the highest dose will be considered the maximum safe dose examined in the study.

6.5 Dosing Delays / Dose Modifications

There are no adjustments for dose delay for a given patient, and treatment delays of >14 days from the treatment plan will not be allowed. If a patient experiences a DLT, treatment of that patient will be suspended. A subject may be considered for receiving further injections of the G100 investigational drug product on a case-by-case basis after the PI and medical monitor, in consultation with the independent DMC, have evaluated the risk/benefit ratio for a subject. As an example, for subjects who have experienced a tumor response and had a non-life- and non-organ-threatening DLT, continuation of treatment as per protocol may be considered.

7.0 SELECTION OF PATIENTS

This study plans to enroll patients with follicular NHL and other indolent lymphomas. In Part 1, Dose Escalation, up to 12 evaluable patients may be enrolled. In Part 2, for the Patient Expansion With or Without Pembrolizumab group, up to 24 additional patients and for the optional Large Tumor Group up to 4 evaluable patients will be enrolled. In Part 3, G100 Expansion of 20 µg Dose Group, up to 25 patients may be enrolled. In Part 4, Sequential G100 at 20 µg/lesion Into Single Or Multiple Tumor Masses Plus Pembrolizumab Group, 22 efficacy

evaluable patients will be enrolled. In Part 5, G100 Plus Rituximab, 12-24 patients will be enrolled during Dose Escalation and 20 efficacy evaluable patients, during Patient Expansion.

